**Hyperpolarized Xenon gas MR Imaging in Radiotherapy**

[figure not shown]
All patients enrolled with lung cancer will undergo clinical assessment involving objective physiological measures (pulmonary function testing and pulse oximetry) and patient orientated functional measures (dyspnoea scores, CTCAE version 4. Radiotherapy-induced lung toxicity assessment) at baseline, on the final day of radiotherapy treatment and 3 months post treatment. These assessments will not be completed at the two week following commencement of radiotherapy schedule visit.

Patients to be treated with radiotherapy affecting the lung that do not have lung cancer, such as oesophageal cancer, chest wall tumours, lymphoma affecting the mediastinum and others, will undergo clinical assessment (excluding full pulmonary function testing) and Xe-129 lung MRI imaging only at each visit.

[figure not shown]
Participation in these full tests takes up to a day, allowing patients time to rest between tests. All participants will be monitored for at least 30 minutes after the final hyperpolarized xenon dose before they are discharged home. It is likely approximately 3 hours will have elapsed since administration of the first hyperpolarized xenon dose by this time. Participants will receive a telephone consultation 24 hours after completion of hyperpolarized Xe-129 MRI to review any AEs that have occurred in the interim following discharge. Furthermore, participants will attend hospital and see the Oncology clinical team on a daily basis during radiotherapy when they will have the opportunity to report any AEs relating to hyperpolarized Xe-129 gas. The study schedule includes follow-up by both the study team and Oncology clinical team in out-patient clinic at regular intervals throughout the 9 month trial duration. This will allow for review of possible AE/SAE two weeks after each hyperpolarized xenon scanning session.

Following the final xenon administration at the 3-month post-radiotherapy follow-up visit, participants will also receive a telephone consultation two weeks later to review AE/SAEs.

## 7.2. Summary Flow Chart of Study Design

**Study schedule for patients with lung cancer diagnosis**

## Study schedule for patients with non-lung cancer diagnosis

## **8. PARTICIPANT IDENTIFICATION**

### **8.1. Trial Participants**

Study participants considered suitable for radiotherapy or chemoradiotherapy (concurrent or sequential schedule) affecting the lung will be recruited.

### **8.2. Inclusion Criteria**

- Participant is willing and able to give informed consent for participation in the trial.
- Male or Female, aged 18 years or above.
- Patients where radiotherapy or chemoradiotherapy (concurrent or sequential schedule) affecting the lung is considered appropriate by the treating clinical Oncologist.
- WHO performance status 0-2
- Able (in the Investigators opinion) and willing to comply with all study requirements.

### **8.3. Exclusion Criteria**

The participant may not enter the trial if ANY of the following apply:

- Inability to give written informed consent.
- Female participant who is pregnant, lactating or planning pregnancy during the course of the trial.
- Previous radiotherapy to the chest.
- The presence of another condition where the disease itself or treatment may interfere with the study endpoints.
- Any psychological, familial, sociological or geographical condition potentially hampering compliance with the study protocol and follow-up schedule.
- Inability to lie flat for imaging.
- Contraindications to MRI examination including indwelling pacemaker, non-MRI compatible metallic implant, severe claustrophobia, intra-ocular foreign body.
- Contraindications for gadolinium enhanced lung MRI scan – known hypersensitivity/allergy to the injection of MultiHance (contains gadobenate dimeglumine and small quantities of benzyl alcohol) that is given as part of this scanning or an adverse reaction to an injection given during previous MRI scanning, severe renal impairment.
- Epilepsy requiring on-going medical treatment, or a seizure within the past year.

## **9. TRIAL PROCEDURES**

### **9.1. Recruitment**

**Hyperpolarized Xenon gas MR Imaging in Radiotherapy**

Potential participants will be identified from out-patient Lung cancer or Oncology clinic appointments. Potential participants will be approached by a member of their clinical team within the hospital setting. Any potential participant fulfilling the inclusion criteria will be informed of the trial by a member of their clinical team. If a patient expresses an interest in the study, they will be given a patient information leaflet and will be asked to give their permission to be contacted by the study team. The leaflet will also provide contact details for the study team should the patient wish to initiate contact.

A member of the study team will contact the participant to arrange an enrolment visit (Visit 1). This may be arranged to coincide with a scheduled out-patient clinic appointment for convenience. Enrolment will involve checking that the patient is eligible for the study, completion of informed consent and study registration. This will be an opportunity to discuss the study in detail, familiarise the participant with the Radiology department where the majority of study measures will take place and to complete a “dummy run” of Xe-129 lung MR imaging as previously described in section 7.1.

## **9.2. Informed Consent**

The participant must personally sign and date the latest approved version of the Informed Consent form before any trial specific procedures are performed. This will be done in accordance with the national and local regulatory requirements.

Patients who express an interest in participating in the trial when a member of their clinical team, usually their Oncologist/Respiratory Physician, discusses it with them will be provided with an information leaflet and will be asked to give their permission to be contacted by the study team. The leaflet will also provide contact details for the study team should the patient wish to initiate this contact. Written and verbal versions of the participant information sheet and informed consent form will be presented detailing no less than: the exact nature of the study; the implications and constraints of the protocol; the known side effects and any risks involved in taking part. It will be clearly stated that the participant is free to withdraw from the study at any time for any reason without prejudice to future care, and with no obligation to give the reason for withdrawal.

Patients are given an MRI safety leaflet, and a contact number to discuss any aspect of the visit and scanning prior to giving consent.

The participant will be allowed as much time as wished to consider the information (at least 24 hours with written information to allow the patient to carefully consider participation but avoid any delay of radiotherapy treatment), and the opportunity to question the Investigator, their GP or other independent parties to decide whether they will participate in the study. The informed consent procedure will conform to the ICH guidelines on Good Clinical Practice. This implies that “the written informed consent form should be signed and personally dated by the patient or by the patient’s legally acceptable representatives”. A copy of the signed Informed Consent will be given to the participants. The original signed form will be retained at the study site. A copy of the

**Hyperpolarized Xenon gas MR Imaging in Radiotherapy**

signed Informed Consent will also be scanned onto the Radiology CRIS system and linked to the participant's Xe-129 MR imaging event.

The person who obtained the consent must be suitably qualified and experienced with up to date GCP/informed consent training, and have been authorised to do so by the Chief/Principal Investigator.

**9.3. Screening and Eligibility Assessment**

Potential participants will be approached by their Oncologist or Respiratory Physician within the hospital setting. Any potential participant fulfilling the inclusion criteria will be informed of the trial by a member of their clinical team. If a patient expresses an interest in the study, they will be given a patient information leaflet and will be asked to give their permission to be contacted by the study team. The leaflet will also provide contact details for the study team should the patient wish to initiate contact.

Prior to registration or any study measures being undertaken, documented informed consent will be completed as detailed in section 9.2.

All participants will undergo clinical assessment including medical history and baseline study measures (section 9.5) over 1 -2 hospital visits as outlined below: -

Demographics

The date of birth, gender and smoking habits will be recorded.

Medical History

This forms part of the patient's routine clinical care.

All female participants of child-bearing age will have had pregnancy excluded as part of their routine clinical care in Oncology prior to starting radiotherapy.

**9.4. Randomisation, blinding and code-breaking**

This study is not a randomised trial. All patients undergoing hyperpolarized MR imaging will breathe Xe-129.

**9.5. Baseline Assessments for patients with a diagnosis of lung cancer**

**Arterial oxygen saturations (SaO2)** – measured after a period sitting quietly and resting. The average reading over a two-minute period is recorded.

Pulmonary Function Tests

**Hyperpolarized Xenon gas MR Imaging in Radiotherapy**

Pulmonary function tests will be carried out, including spirometry, lung volumes and carbon monoxide transfer factor. Recordings will be compared to predicted values determined from standard published data.

Spirometry will involve the participant breathing out as fast as they can for as long as they can, at least three times. The maximal amount breathed out in one second (forced expiratory volume in one second, FEV1) and total amount breathed out (forced vital capacity, FVC) will be recorded. Recorded values will be compared to predicted values determined from standard reference tables. Spirometry may be repeated following bronchodilator or steroid therapy to assess for reversibility as indicated by improvement FEV1 if a clinical history of asthma or chronic obstructive pulmonary disease (COPD) is present.

**Analysis** will be based on change in % predicted values over time.

**Dyspnoea**

Dyspnoea (breathlessness) will be measured using the Dyspnoea-12 score (70), a seven-point Likert scale and a visual analogue score.

**Analysis** will be based on the change in score from the baseline over time.

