## 6. OBJECTIVES AND OUTCOME MEASURES/ENDPOINTS

|           | Objectives  | Outcome Measures/Endpoints  |
|-----------|---|---|
| Primary   | To demonstrate that hyperpolarized Xe-129 is sensitive to change following pulmonary radiotherapy, and thus may be developed as an objective and quantifiable method of functional lung assessment in patients undergoing radiotherapy that affects the lung  | Change in hyperpolarized Xe-129 MR imaging from baseline to other time points post radiotherapy initiation.   |
| Secondary | 
To obtain preliminary data demonstrating if changes in hyperpolarized Xe-129 MR imaging correlate with subjective and objective responses following pulmonary radiotherapy.
 
To obtain preliminary data demonstrating if baseline hyperpolarized Xe-129 MR imaging is a more reliable clinical
 | 
Change in hyperpolarized Xe-129 MR imaging parameters from baseline to other time points post radiotherapy initiation compared to subjective and objective measures of lung function.
 
Comparison of hyperpolarized Xe-129 MR imaging and four-dimensional CT (4D-CT) at baseline.
 |

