**Hyperpolarized Xenon gas MR Imaging in Radiotherapy**

|  |   |   |
|--|---|---|
|  | 
indicator of patient respiratory tolerance to pulmonary radiotherapy than conventional lung function testing by determining the relationship between hyperpolarized Xe-129 MR imaging indices and functional patient outcome measures (dyspnoea and radiation-induced lung toxicity assessment).
 
To use functional lung information in virtual predictive and adaptive radiotherapy treatment planning.
 | 
Retrospective comparison of modified radiotherapy treatment planning incorporating functional lung information from hyperpolarized Xe-129 MR imaging with conventional radiotherapy treatment plans.
 |
|--|---|---|

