**Radiation-induced lung toxicity (RILT)**

RILT will be assessed using the common terminology criteria for adverse events (CTCAE version 4). This is completed as part of standard routine care to enable assessment of functional impairment relating to radiotherapy-induced lung toxicity.

**Analysis** will be based on the change in score from the baseline over time.

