#### Demonstration of superiority over standard lung function assessment tools

- Multivariate analysis to correlate global and regional (lobar) data from Xe-129 lung MRI with key patient-centred outcome measures – dyspnoea assessment using the Dyspnoea-

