**Hyperpolarized Xenon gas MR Imaging in Radiotherapy**

12 score (70) and MRC breathlessness score. We will test the hypothesis that Xe-129 lung MRI has a closer correlation with these measures than FEV1 or gas transfer.

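### Dyspnoea is analysed as change from baseline with no baseline covariate specified, so prediction from baseline Xe-129 MRI or lung function can be hidden, inverted or mis-ranked

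*Combined protocol and SAP*

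**What the plan says.** Section 9.5 (Dyspnoea) lists Dyspnoea-12, a Likert scale and a visual analogue score, and states that analysis "will be based on the change in score from the baseline over time". The RILT paragraph of 9.5 uses the same sentence for CTCAE version 4 scores, without listing the CTCAE terms to be graded.

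Section 6 has two secondary objectives that use these outcomes. The first relates changes in Xe-129 MRI to subjective and objective responses. The second is "To obtain preliminary data demonstrating if baseline hyperpolarized Xe-129 MR imaging is a more reliable clinical" indicator of tolerance than conventional testing, to be met by "determining the relationship between hyperpolarized Xe-129 MR imaging indices and functional patient outcome measures", namely dyspnoea and RILT. In the second objective the predictor is a baseline value.

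For the comparison with standard tests, section 12.1 plans "Multivariate analysis to correlate global and regional (lobar) data from Xe-129 lung MRI with key patient-centred outcome measures" and adds: "We will test the hypothesis that Xe-129 lung MRI has a closer correlation with these measures than" FEV1 or gas transfer. Section 9.5 plans a similar analysis against Dyspnoea-12 and RILT. Neither states covariates, visit, or whether the outcome is a level or a change.

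**The concern.** A change score contains the baseline score with a minus sign. A high baseline tends to be followed by a smaller rise or a fall, so change correlates negatively with its own baseline. An index that tracks baseline breathlessness inherits part of that negative correlation. It can then look inversely related to later deterioration when it adds nothing, or look useless when it does add prediction.

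The distortion grows with the index's correlation with baseline dyspnoea. Xe-129 MRI, FEV1 and gas transfer need not share that correlation, so a test of which index correlates more closely could be settled by the choice of outcome. The condition is plausible here, because section 12.1 presupposes that these indices relate to breathlessness.

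**Working it through.** **Inputs from the documents.** Total sample size 30 (12.2) and significance level 0.05 (12.3). Section 12.2 gives no power, effect size, SD or correlation, so there is no planned figure to reproduce. Sidedness is not stated.

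**Assumptions.** Two-sided test; equal SDs at baseline and follow-up unless stated; all correlations. X is the baseline index, oriented so that higher goes with more dyspnoea. Y0 and Y1 are baseline and follow-up dyspnoea. Write r0 = corr(X,Y0), r1 = corr(X,Y1), r = corr(Y0,Y1).

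**Formulas.**
- Correlation with change: (r1 − r0) / sqrt(2 − 2r)
- Partial correlation given baseline: (r1 − r × r0) / sqrt((1 − r0²)(1 − r²))
- Rejection probability: Φ(z − 1.96) + Φ(−z − 1.96), where z = atanh(correlation) × sqrt(n − 3), or sqrt(n − 4) for the partial correlation

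**1. No added prediction.** Here r1 = r × r0, so the partial correlation is 0 and the correlation with change becomes −r0 × sqrt((1 − r)/2). With r0 = 0.5 and n = 30:
- r = 0.4: −0.5 × sqrt(0.3) = −0.27, rejection 31%
- r = 0.6: −0.5 × sqrt(0.2) = −0.22, rejection 22%
- r = 0.8: −0.5 × sqrt(0.1) = −0.16, rejection 13%

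The adjusted test stays at 5%. A simulation of a similar case (r0 = 0.5, r1 = 0.25, r = 0.5; 10,000 runs) rejected in 27.9% unadjusted and 5.1% adjusted.

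**2. Real added prediction, n = 30, r = 0.6.**

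| r0 | r1 | Corr. with change | Power | Partial corr. | Power |
|---|---|---|---|---|---|
| 0.5 | 0.525 | 0.025/0.894 = 0.03 | 5% | 0.225/0.693 = 0.325 | 40% |
| 0.4 | 0.4 | 0 | 5% | 0.22 | 21% |
| 0.2 | 0.4 | 0.2/0.894 = 0.22 | 22% | 0.28/0.784 = 0.36 | 48% |
| 0.5 | 0.6 | 0.1/0.894 = 0.11 | 9% | 0.3/0.693 = 0.43 | 66% |
| 0 | 0.4 | 0.4/0.894 = 0.45 | 71% | 0.4/0.8 = 0.50 | 80% |

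The first row lies close to exact cancellation. The last is the mild case, an index unrelated to baseline dyspnoea.

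**3. Ranking.** Compare the third and fourth rows. On change, the (0.2, 0.4) index leads by 0.22 to 0.11. Given baseline, the (0.5, 0.6) index leads by 0.43 to 0.36.

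**4. RILT.** With r0 = r1 = 0.4, r = 0.6 and baseline SD equal to s times the follow-up SD, the correlation with change is 0.4(1 − s)/sqrt(1 + s² − 1.2s). This gives 0.40 at s = 0, 0.38 at 0.1, 0.34 at 0.25, 0.25 at 0.5 and 0 at 1. With almost no baseline variation there is almost no distortion.

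**5. Numbers available.** Full pulmonary function tests are done only in lung cancer patients (7.1, 9.6). Only one follow-up visit is compulsory (7.1), and the half-way visit records no dyspnoea (9.8, 9.9). The FEV1 and gas-transfer comparison is therefore likely to have fewer than 30 patients. If n were 20, the mild case would fall to 51% against 59%.

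**The case against.** **No unadjusted model is stated.** A reader might infer that section 9.5 fixes raw change as the outcome of the predictive analysis. It does not go that far. The sentence is a one-line description of a measure, and it suits the change-versus-change objective. The multivariate analyses are unspecified and do not rule out a baseline covariate. If change is the outcome and baseline is a covariate, adding Y0 to both sides gives the model for Y1, with the same coefficient for X. This stands: the defect is a missing specification. But change is the only rule given, and nothing requires the covariate.

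**RILT.** The identical sentence under RILT might suggest the same distortion there. Section 8.3 excludes "Previous radiotherapy to the chest", so a radiation-induced grade should be near zero at baseline and change is then close to the follow-up grade. Distortion would need CTCAE terms that pick up pre-existing symptoms, and the terms are not listed. What remains is that subtraction treats ordinal steps as equal.

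**Adjustment is not neutral.** Suppose the index tracks stable underlying dyspnoea and the two scores differ only by measurement error. At r0 = r1 = 0.5 and r = 0.6, the correlation with change is 0. The partial correlation is 0.2/sqrt(0.75 × 0.64) = 0.29, with about 33% rejection at n = 30, although the index is unrelated to true change. This counts if true deterioration is the target. For prediction, conditioning on the observed baseline is the right target. It is a reason to report both analyses.

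**Preliminary aim.** The objective seeks preliminary data and no power is claimed. That limits the importance of the point, but not the case for a clear model.

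**Conclusion.** The concern holds for dyspnoea in the objective that uses a baseline predictor. The only stated basis is change from baseline and no baseline covariate is specified. An unadjusted analysis could miss added prediction, show a false inverse association or choose the wrong index, whenever the indices relate to baseline dyspnoea.

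The percentages are illustrations under assumed correlations, equal SDs and n = 30. They should not be read as operating characteristics of this trial, because the documents give no correlations. The loss is small if an index is unrelated to baseline dyspnoea, and power stays low in several cases even after adjustment. The point does not touch the primary endpoint or the change-versus-change objective, and the regression-to-the-mean argument does not carry over to RILT where baseline grade is near zero. It should be corrected, with weight proportionate to a secondary, preliminary objective.

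**What to change.** For analyses with a baseline predictor, add to section 12.1:
- Outcome: Dyspnoea-12 at one named visit, either the final day of radiotherapy or 3 months after it.
- Model: linear regression on the predictor with baseline Dyspnoea-12 as covariate.
- Comparison: the same model and the same patients for Xe-129 MRI, FEV1 and gas transfer, with that number reported.
- Sensitivity analysis: the unadjusted change score.

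Keep change scores for the change-versus-change objective. For RILT, analyse the follow-up CTCAE grade as an ordinal outcome without subtracting baseline, and list the CTCAE terms graded.

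The cost is a few sentences. Baseline dyspnoea is already scheduled in both diagnostic groups (9.5, 9.6). The adjusted model uses one degree of freedom, and in this non-randomised cohort its result describes prediction given the observed baseline score, not true change. The report should say so.

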**Radiation-induced lung toxicity (RILT)**

RILT will be assessed using the common terminology criteria for adverse events (CTCAE version 4). This is completed as part of standard routine care to enable assessment of functional impairment relating to radiotherapy-induced lung toxicity.

**Analysis** will be based on the change in score from the baseline over time.

**Ventilation/perfusion nuclear medicine scan (SPECT/CT)**

Ventilation/perfusion nuclear medicine scan will be completed at baseline only and is an optional study measure. This scan is performed using the 16-slice GE Discovery 670 scanner as per local protocol. The nuclear medicine scan involves three components: -

- Ventilation imaging – this involves the patient breathing in a gaseous tracer in aerosol form e.g. technetium-labeled diethylenetriamine pentaacetate (99mTc-DTPA) via a mouthpiece or mask.
- Perfusion imaging – this involves insertion of a cannula, and then an injection of a small volume, < 5 mL, of radioactive technetium labelled macro aggregates of albumin (99mTc-MAA). A gamma camera acquires images for both ventilation and perfusion components. Patients do not have to move to a different bed between the nuclear medicine and CT scans, so it is associated with minimum disruption.

Participants will be screened for contraindications to nuclear medicine scanning including known hypersensitivity to albumin or preference to avoid blood donation product. If a contraindication

**Hyperpolarized Xenon gas MR Imaging in Radiotherapy**

to the nuclear medicine scan is identified, it will not be performed. This will not exclude the patient from participating in the study.

**Computed Tomography (CT)**

Thoracic CT will be performed at the Churchill Hospital. An injection of iodinated contrast will be administered through the same cannula that was inserted for the nuclear medicine scan. Scanning takes place 50-60 seconds post injection as per standard imaging protocol. CT images will be acquired during a single breath hold performed triggered to lung volume. The patient lies on their back, whilst scanning takes place.

Participants will be screened for contraindications to iodinated contrast prior to completion of this study measure. These include: -

- Marked renal failure not on dialysis
- Known allergy to contrast medium, history of anaphylaxis
- Known or suspected thyroid carcinoma
- Inability to gain intra-venous access

If contraindication to iodinated contrast is identified, all thoracic CT scans will be performed without contrast. This will not exclude the patient from participating in the study.

Software will be used to determine areas of lung attenuation, such as delineating areas < -950 HU validated by visual inspection by an experienced thoracic radiologists, and/ or other measures of local texture in CT imaging. Comparisons with manual region of interest performed on an image display software (OsiriX) will be made.

